8.2. Background Characteristics

8.2.1. Participant Disposition

The summary of disposition will use the All Participants Set and include number of participants who were screened, screen failed, successfully screened but did not dose, and successfully screened and dosed (overall and by previous study participation), and, using the number of participants who successfully screened and dosed as the denominator, the number and percentage of participants who completed treatment, who discontinued treatment (overall, by dose level, and by primary reason for discontinuing treatment), who completed the study, and who discontinued the study (overall and by primary reason).

If a participant is rescreened because he/she has been a screen failure the first time, the status of the participant will be determined from the second screening. In the count of screened participants, such a participant will be counted only once.

A completer of the study is a participant with the study completion question answered 'Yes' on the End of Study / Study Disposition CRF page. A completer of treatment is a participant with the treatment completion question answered 'Yes' on the IP Completion / Discontinuation CRF page. The primary reason for discontinuing the study is provided in the respective CRF page.

The number of participants in each of the analysis sets will also be summarized and presented, using the All Participants Set. The reasons for participants being excluded from each analysis set will be listed (using All Participants) but not summarized.

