2. SYNOPSIS

Name of Sponsor/Company: Sage Therapeutics, Inc. (hereafter referred to as Sage Therapeutics, or Sage)										
Name of Investigational Product: SAGE-324 Oral Tablet										
Name of Active Ingredient: SAGE-324										
Title of Study: An Open-label Study of the Long-term Safety and Tolerability of SAGE-324 in Participants with Essential Tremor										
Number of Sites and Study Location: This study will take place at approximately 50 sites in the United States (US)										
Phase of Development: 2/3										
Planned Duration for Each Study Participant: The duration of participation (from Screening through the final Follow-up Visit) for each participant will be until marketing authorization, projected to be up to approximately 5 years.										
Objectives and Endpoints: 

Objectives	Endpoints	

Primary		

To assess the long-term safety and tolerability of SAGE-324	
Incidence of treatment-emergent adverse events (TEAEs)	

Secondary		

To assess the long-term effect of SAGE-324 on other safety parameters	
Change from baseline in vital signs, electrocardiogram (ECG), clinical laboratory parameters, Epworth Sleepiness Scale (ESS), and Columbia-Suicide Severity Rating Scale (C-SSRS) responsesPhysician Withdrawal Checklist (PWC-20) scores	

	Objectives	Endpoints	Primary		
To assess the long-term safety and tolerability of SAGE-324	
Incidence of treatment-emergent adverse events (TEAEs)	Secondary		
To assess the long-term effect of SAGE-324 on other safety parameters	
Change from baseline in vital signs, electrocardiogram (ECG), clinical laboratory parameters, Epworth Sleepiness Scale (ESS), and Columbia-Suicide Severity Rating Scale (C-SSRS) responsesPhysician Withdrawal Checklist (PWC-20) scores
Objectives	Endpoints									
Primary										

To assess the long-term safety and tolerability of SAGE-324	
Incidence of treatment-emergent adverse events (TEAEs)									
Secondary										

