- ^c ECGs will be collected and read locally. All ECGs must be performed after the participant has been in a supine position for at least 5 minutes.
- ^d Chemistry, hematology, coagulation, and urinalysis at Screening and at all additional timepoints. Myoglobin (urinalysis) and serum creatine kinase (biochemistry) at Screening and at additional timepoints at the discretion of the investigator. A serum sample for blood alcohol level will be collected at Screening and all additional timepoints. HgA1c will be collected at Week 12 and Week 24.
- [REDACTED]
- ^f If a participant experiences AEs at any time during the Treatment Period that are considered by the investigator to be related to the IP and not tolerable, the investigator may reduce the dose of IP in 15 mg decrements. Self-administration of IP will be interrupted for 3 to 8 days before the initiation of the reduced dose.
- ^g Participants will self-administer on an outpatient basis a single dose of SAGE-324 once daily in the evening before bed, with a snack if bedtime is not within 2 hours of the evening meal.

Table 4: Schedule of Assessments: Month 9 to Follow-up Period

Assessment	Treatment Period						Follow-up Period	
	Month 9	Month 12	Month 15	Month 18	Month 21	Month 24 to Month 60 (Every 3 Months)	EOT 3 (± 3) days after last dose of SAGE-324	EOS 14 (± 3) days after last dose of SAGE-324
Study Month								
Window (Weeks)	± 2							
Pregnancy test	X (urine; WOCBP only)	X (urine; WOCBP only)	X (urine; WOCBP only)	X (urine; WOCBP only)				
Complete physical examination, including neurological examination including MSE ^a	X	X	X	X	X	X	X	X
Body weight ^b		X				X		X
Vital signs ^c	X	X	X	X	X	X	X	X
12-Lead ECG ^d	X	X	X	X	X	X	X	X
Chemistry/hematology/ coagulation/urinalysis ^e	X	X	X	X	X	X	X	X
C-SSRS ("Since Last Visit" form)	X	X	X	X	X	X	X	X
ESS	X	X	X	X	X	X	X	X
PWC-20							X	X
Dispense SAGE-324 ^f	X	X	X	X	X	X		

Assessment	Treatment Period						Follow-up Period	
	Month 9	Month 12	Month 15	Month 18	Month 21	Month 24 to Month 60 (Every 3 Months)	EOT 3 (± 3) days after last dose of SAGE-324	EOS 14 (± 3) days after last dose of SAGE-324
Study Month								
Window (Weeks)	± 2	± 2	± 2	± 2	± 2	± 2		
SAGE-324 accountability	X	X	X	X	X	X	X	X
SAGE-324 administration ^h	Administered once daily before bed							
AEs/SAEs	X							
Concomitant medication	X							

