Participants should gain experience with the study drug to see how it affects them before engaging in potentially hazardous activities requiring mental alertness, such as driving. If participants experience any sleepiness, dizziness, or feelings of relaxation, or have other sedative effects, they should not engage in potentially hazardous activities requiring mental alertness, such as driving, until any sleepiness/sedative effects from the study drug have dissipated. This is important because study participants may not be able to judge how these sedative effects will affect their ability to perform potentially hazardous activities requiring mental alertness, including driving.

The Treatment Period will continue for as long as the participant continues to self-administer SAGE-324 or until marketing authorization, projected to be up to approximately 5 years.

Follow-Up Period:

Follow-up visits will be conducted on an outpatient basis when participants have completed the Treatment Period. Participants will continue to complete questionnaires as indicated in [Table 4](#) and will return to the clinic 3 (± 3) days after the last dose of SAGE-324 for safety, tolerability, [REDACTED] at the End of Treatment (EOT) Visit. Participants will return to the study center for an End of Study (EOS) Visit, 14 (± 3) days after the last dose of SAGE-324.

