7.5. Criteria for Study Termination

Sage Therapeutics may terminate this study or any portion of the study at any time for safety reasons including the occurrence of AEs or other findings suggesting unacceptable risk to participants, or for administrative reasons. In the event of study termination, Sage Therapeutics will provide written notification to the investigator. Investigational sites must promptly notify their institutional review board (IRB)/independent ethics committee (IEC), where required, and initiate withdrawal procedures for participating participants.

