7.6. End of Study Definition

The end of the study is defined as the date of the last visit of the last participant in the study. A participant is considered to have concluded the study if he/she has completed dosing and completed the EOS Visit as per the Schedule of Assessments ([Table 4](#)) or is lost to follow-up.

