5. STUDY DESIGN

5.1. Overall Design

This study is an open-label study to evaluate the long-term safety and tolerability of SAGE-324 in participants with Essential Tremor (ET) who have completed the planned End of Treatment (EOT) Visit and who were not early terminated during the planned Treatment Period in another SAGE-324 study. This study includes a Screening Period of up to 28 days, a Treatment Period with weekly outpatient visits for the first 8 weeks, outpatient visits on Weeks 10, 12, 16, 20, and 24, and quarterly outpatient visits thereafter to the end of dosing, and a 14-day Follow-up Period. See the Schedule of Assessments ([Appendix A](#)) for the full list of study assessments and timings. The study is schematically presented in [Figure 1](#).

Participants who have provided informed consent will undergo screening assessments up to 28 days prior to the planned day of dosing. Eligible participants will complete additional eligibility and baseline assessments.

[figure not shown]
Starting on Day 1, participants will self-administer on an outpatient basis a single dose of SAGE-324 once daily in the evening before bed, with a snack if bedtime is not within 2 hours of the evening meal. The dosing will start at 15 mg, and according to the dose escalation schedule provided in Figure 1 below, will be escalated to 60 mg starting on Day 43. If a participant experiences adverse events (AE) at any time during the Treatment Period that are considered by the investigator to be related to the investigational product (IP) and not tolerable, the investigator may reduce the dose of IP in 15 mg decrements, including during the initial dose escalation period. Administration of IP will be interrupted for 3 to 8 days before the initiation of the reduced dose.

During the Treatment Period, participants will return to the study center for safety, tolerability [REDACTED] as specified in [Appendix A](#). In addition, safety phone call study visits will be conducted as deemed appropriate by the investigator to review the current status of the participant. Participants will be trained in the use of software applications and devices necessary to complete questionnaires and/or self-rated study assessments.

The Treatment Period will continue for as long as the participant continues to self-administer SAGE-324 or until marketing authorization, projected to be up to approximately 5 years.

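### Crude completion and discontinuation percentages in SAP 8.2.1 mix the discontinuation rate with unequal follow-up, most severely by dose level, and no event defines completed treatment

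*SAP*

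**What the plan says.** **Length of treatment.** Protocol 7.1 states: "The Treatment Period will continue for as long as the participant continues to self-administer SAGE-324 or until marketing authorization", and SAP 5.1 repeats this with a projection of up to about five years. The synopsis says that the duration of participation "for each participant will be until marketing authorization, projected to be up to approximately 5 years". On-treatment visits are scheduled through the column headed "Month 24 to Month 60 (Every 3 Months"). Separately, Protocol 7.5 says that "Sage Therapeutics may terminate this study or any portion of the study at any time for safety reasons", and it also allows termination for administrative reasons.

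**Disposition.** SAP 8.2.1 takes everyone successfully screened and dosed as the denominator and reports "the number and percentage of participants who completed treatment, who discontinued treatment (overall, by dose level, and by primary reason for discontinuing treatment"). The definition is: "A completer of treatment is a participant with the treatment completion question answered 'Yes" on the IP completion or discontinuation CRF page. Protocol 7.6 is nearby but does not supply the missing definition: "A participant is considered to have concluded the study if he/she has completed dosing and completed the EOS Visit" concerns concluding the study, and it uses completed dosing without saying what that means.

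**Dose steps.** Protocol 7.3 plans 14 days each at 15, 30 and 45 mg, then 60 mg from Day 43 with no planned end.

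**Time information that the SAP does give.** SAP 8.2.6 summarizes total exposure duration, overall and by dose at treatment discontinuation. The visible text and display list contain no time-to-discontinuation analysis, no retention at fixed times and no rate per person-year.

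**The concern.** A percentage discontinued can be interpreted when everyone has the same planned treatment period. Here nobody does. A participant who enters a year before closure has one year in which to discontinue, and a participant who enters five years before closure has five. One percentage over both describes the drug and the calendar together. With no control arm, no comparator shares the same follow-up pattern and could help to separate the two.

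The by-dose split adds a second problem. Planned time at risk is two weeks at each lower dose and possibly years at 60 mg. Discontinuations will accumulate at 60 mg even if the dose has no effect on tolerability, and a reader could take that for dose-related intolerance.

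Thirdly, the visible text does not say how to classify a participant who is still taking drug when the sponsor ends dosing. That group could be large, so the completed percentage depends on how one CRF question is answered for them.

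**Working it through.** **Inputs.** From the documents: open-ended treatment (Protocol 7.1, SAP 5.1), schedule to Month 60 (Protocol Table 4), 14-day steps at 15, 30 and 45 mg and 60 mg from Day 43 (Protocol 7.3), denominator of all dosed (SAP 8.2.1). The documents give no discontinuation rate, accrual period or closing date. The only related figure is the sample size of about 750, stated without inputs, so there is no plan figure to reproduce. Every hazard and follow-up pattern below is an assumption.

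**1. Effect of follow-up at a fixed hazard.** With constant hazard h and common follow-up t, the crude proportion discontinued is 1 − exp(−ht).
- 3% per month: 1 − exp(−0.03 × 12) = 30.2%; 1 − exp(−0.03 × 60) = 83.5%.
- 2% per month: 21.3% and 69.9%. 5% per month: 45.1% and 95.0%.

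**2. Both influences together.** Crude % discontinued by annual hazard and years of follow-up:

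| h per year | 0.5 y | 1 y | 2 y | 3 y | 5 y |
|---|---|---|---|---|---|
| 0.1 | 4.9 | 9.5 | 18.1 | 25.9 | 39.3 |
| 0.25 | 11.8 | 22.1 | 39.3 | 52.8 | 71.3 |
| 0.5 | 22.1 | 39.3 | 63.2 | 77.7 | 91.8 |
| 1.0 | 39.3 | 63.2 | 86.5 | 95.0 | 99.3 |

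Rows show follow-up moving the figure, and columns show the hazard moving it.

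**3. Staggered entry.** With follow-up uniform from a to b, the crude proportion is 1 − [exp(−ha) − exp(−hb)] / [h(b − a)].
- 3% per month, entry over 24 months: closure at 36 months (follow-up 12 to 36) gives 50.3%; closure at 60 months (36 to 60) gives 75.8%.
- h = 0.25 per year over 0 to 2 years: 1 − [1 − exp(−0.5)] / 0.5 = 21.3%. h = 0.5 per year over 0 to 1 year gives the same expression, so also 21.3%. A twofold difference in rate cannot be seen.

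**4. Front-loaded discontinuation.** With 1.5 per year for 84 days and 0.15 per year afterwards, the crude figure is 32.0% at 0.5 year and 65.4% at 5 years. The dependence is weaker but remains.

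**5. By dose level.** Assume h = 0.25 per year at every dose, the planned titration without reductions, and 2 years of follow-up. The share discontinuing in each step is exp(−h t0) − exp(−h t1), with cut points at 14, 28 and 42 days and 2 years: 1.0% at 15 mg, 0.9% at 30 mg, 0.9% at 45 mg and 36.5% at 60 mg (total 39.3%, as in step 2). The ratio of 60 mg to 15 mg is about 38, from time at risk alone.

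**6. Rate per person-year.** Simulation with 750 participants and 2,000 runs, h = 0.25 per year:

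| Follow-up, years | Crude % | Events per person-year (SD) |
|---|---|---|
| 0 to 1 | 11.5 | 0.250 (0.027) |
| 0 to 2 | 21.2 | 0.249 (0.020) |
| 3 to 5 | 62.9 | 0.251 (0.011) |

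The rate recovers the assumed value in each case. In step 5, expected person-time in each step equals expected events divided by h, so the rate is 0.25 per year at every dose. Kaplan-Meier estimation was not simulated.

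**7. Completion.** With h = 0.25 per year and 0 to 2 years of follow-up, 100% − 21.3% = 78.7% are on drug at closure. If all of them are answered Yes, completion is 78.7%; if all are answered No, it is 0%.

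**The case against.** The strongest reply is that this is a descriptive, single-arm plan. The primary endpoint is the incidence of TEAEs (SAP 4.1), disposition sits under background characteristics, and TEAEs leading to IP discontinuation are tabulated separately (SAP 8.4.1). Exposure duration is also summarized. The hazards are assumed, and a constant hazard is doubtful with a six-week titration. The CRF page and its instructions are not visible and may define completion.

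Much of this stands. Disposition is supporting tolerability evidence, and the sizes are illustrations. The TEAE-discontinuation percentages, however, are also crude, and exposure summaries do not treat participants still on drug as censored. They therefore give partial context, not retention at a given time.

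A reader might go further than the documents allow in three ways:
- **That the figure reflects time since enrolment and not the drug.** At two years it runs from 18.1% to 86.5% as the hazard goes from 0.1 to 1.0 per year. Both matter, and the crude percentage cannot separate them.
- **That treatment ends for everyone at one calendar event.** Participants may stop individually, the schedule ends at Month 60, and the sponsor may terminate all or part of the study earlier.
- **That someone who stops at Month 3 counts as a completer, because the Treatment Period lasts only as long as dosing.** This reading is strained: the synopsis gives a planned duration, and the SAP tabulates reasons for discontinuing. The supportable statement is narrower: the classification of participants on drug at closure is unclear.

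**Conclusion.** The point holds as an analysis improvement that should be made. SAP 8.2.1 reports crude percentages over unequal, open-ended follow-up, and nothing in the visible text adjusts for it. The by-dose percentages are the most open to misreading. Completed treatment is not tied to any event or duration in the visible text.

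The size depends on quantities that the documents do not give. Under the assumptions shown, changing only follow-up moves the crude figure from 30.2% to 83.5% at 3% per month, and equal hazards produce a roughly 38-fold gap between 60 mg and 15 mg. Front-loaded discontinuation reduces the first effect (32.0% at half a year to 65.4% at five years). Parts of the SAP, including Section 8.3 and some displays, are redacted or removed, so absence is judged on what can be read. The primary endpoint is not affected by this point.

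**What to change.** Keep the existing counts and make three changes.

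- **Closure category (8.2.1).** Report participants on IP when dosing ends by sponsor closure, or at Month 60, as their own category. Split closure by reason (authorization, administrative, safety), so that a safety termination is not counted as completion.
- **Time to discontinuation.** Add Kaplan-Meier estimates for all-cause IP discontinuation at fixed times, for example Weeks 6, 12 and 24 and Months 12 and 24, with numbers at risk and with participants on IP at closure censored. Add the cumulative incidence of discontinuation due to AE, with other reasons as competing events. State the assumption that entry date is unrelated to discontinuation risk.
- **By dose.** Replace or accompany the by-dose percentages with discontinuations per person-year at each dose. State how days of interruption before a dose reduction are attributed.

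The cost is one SAP paragraph and one or two displays. First and last dose dates, dosing records and reasons for discontinuation are already collected, so no new data collection is needed.

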8.2.2. Protocol Deviations

Protocol deviations will be captured on eCRF and categorized by the study team as major and minor deviations. The major deviations will be summarized by type using the Safety Set. The minor deviations will be included in the listing but not summarized. The COVID-19 related protocol deviations will be summarized separately.

Inclusion/exclusion violations will be listed for All Participants (excluding screen failures) but not summarized.

8.2.3. Demographics and Baseline Characteristics

Demographic data (age, sex, race, and ethnicity), baseline characteristics (height, weight, BMI, dominant upper limb), [REDACTED]

[REDACTED] will be summarized with descriptive statistics using the Safety Set.

Baseline subgroups will be summarized for the following categories:

- Race (Black or African American, White, Asian, Other)
- Sex (Female, Male)
- Age (<65, 65 to 80 years)
- BMI (<18.5, 18.5 to <25, 25 to <30, ≥ 30 kg/m²)

[REDACTED]
[REDACTED]

Listings will be provided for demographics, other baseline characteristics, and informed consent data.

8.2.4. Medical/Surgical History

Medical/surgical history will be coded to Medical Dictionary for Regulatory Activities (MedDRA) terms, using Version 25, or higher. The MedDRA version will be included in the footnotes of related outputs. Medical/surgical history will be summarized using discrete summary statistics for each MedDRA System Organ Class (SOC) and Preferred Term (PT) using the Safety Set.

Age at ET diagnosis (years), age participant thinks ET started (years), years with ET diagnosis (age at baseline minus age at ET diagnosis), years since participant thinks ET started (age at baseline minus age when participant thinks ET started), tremor responsive to alcohol, past treatments for ET, and response to past treatment for ET will be summarized using the Safety Set. The data listing will also include reason for discontinuation from the past treatment.

The disease history will be summarized for the following categories:

- Age at ET diagnosis (<40 years, 40 to 60 years, >60 years)
- Age participant thinks ET started (<20 years, 20 to 40 years, >40 to 60 years, >60 years)
- Years with ET diagnosis (3 to <6 years, 6 to 10 years, >10 years)
- Years since participant thinks ET started (3 to <6 years, 6 to 10 years, >10 years)
- Tremor responsive to alcohol: Yes (Intermediate, Worked Well), No (No, a little), NA
- Past treatment for ET (Yes, No)
- Response to past treatment for ET: Yes (Intermediate, Worked Well), No (No, a little), Yes and No (denominator for percentages will be participants having past treatment for ET)

8.2.5. Prior and Concomitant Medications

Medications will be recorded at each study visit and coded into drug class (anatomical therapeutic chemical [ATC] Level 2) and PT using World Health Organization-Drug dictionary (WHO-DD) Global B3 March 2022, or later.

All medications taken within 30 days prior to informed consent through the duration of the study (including start and end dates, route, dose/units, frequency, and indication) will be recorded on the electronic case report form (eCRF).

Those medications taken prior to the initiation of the IP will be denoted “Prior”. Those medications taken prior to the initiation of the IP and continuing beyond the initiation of the IP or those medications started at the same time or after the initiation of the IP will be denoted “Concomitant”. Note that medication taken before the initial dosing of IP and continued after the initial dosing will be categorized as a prior medication and separately as a concomitant medication.

Medications will be flagged in the listing according to whether they are “Prior” or “Concomitant” as defined above. In the event of a missing start or stop date associated with a medication, only the classification (prior and/or concomitant) will be imputed using the algorithm described in [Appendix B](#). Dates will not be imputed.

Prior and concomitant medications will be summarized separately using the Safety Set as the number and percentage of participants with each medication at both the ATC and PT levels. Concomitant procedures will be listed with SOC/PT, but not summarized.

